#### E.10. Case Report Forms, Data Capture and Source Documentation

Case report forms are provided for each subject in electronic format. Research Electronic Data Capture (REDCap), developed at Vanderbilt University but widely used internationally, is a secure, web-based application designed to support data capture for research studies. REDCap provides: 1) an intuitive interface for data entry (with data validation); 2) audit trails for tracking data manipulation and export procedures; 3) automated export procedures for seamless data downloads to common statistical packages (SPSS, SAS, STATA, R); 4) procedures for importing data from external sources; and 5) advanced features, such as branching logic and calculated fields within electronic forms and the survey feature. Data will be uploaded securely from each research site via REDCap.

Electronic source documentation must be made available to confirm data collected properly. In the event that a paper version CRF was used as the primary medium for data collection at any study site, and subsequently entered into REDCap, the paper CRF will serve as the source document. Source document data includes author initials and date of entry to source documentation. Also, the necessary fields for source documentation review are subject identification code, eligibility, study identification, study discussion and date of signed informed consent, dates of visits, record of all UPIRTSO and non-UPIRTSO and results of reporting, concomitant medications, drug order and dispensing records (de-identified), study drug administration information, date subject completed or discontinued study, date and reason study drug was discontinued early, if applicable. Subject measures completed by subject, investigator or subject personnel will also be considered source documents. It will be the responsibility of the investigator to verify that all data entries in the CRFs are accurate and correct.

### **E.11. Data Safety Monitoring Plan and Board**

Monitoring responsibilities for this study will be assigned to investigators [name] (Mayo Clinic), [name] (University of Michigan), [name], CCRP (Mayo Clinic) or appropriate designee determined by the sponsor. Neither investigator will serve to monitor their own site. Three on-site monitoring visits will be made: pre-initiation, post-initiation and a close-out visit at each site. In addition, either of the investigator monitors will perform the on-site monitoring visits as frequently as necessary. The designated investigator monitor will record dates of the site visits in a study site visit log that will be kept at the study site. The post-initiation visit will be scheduled after enrollment of the 3rd subject has occurred at each site and the close-out visit will occur once recruitment is completed.

At these visits, the investigator monitor will compare the entered CRF data with the source documents. The nature and location of all source documents will be identified to ensure that all sources of original data required to complete the CRF are known to the investigator monitor and study-site personnel, and are accessible for verification by the investigator monitor and study-site personnel. If electronic records are maintained at the study site, the method of verification must be discussed with the investigator monitor and a report will be generated.

Investigator monitor visit expectations include the availability of the study-site personnel, accessible source documentation, and a suitable environment for review of study-related documents. The investigator monitor will meet or correspond with the Site Lead Investigator during the study to provide feedback on the study conduct.

The Bio-K Data Safety Monitoring Board (DSMB) shall have the responsibility to review on a scheduled basis accumulating data and monitoring reports from all sites. The DSMB advises the sponsor NNDC regarding the continuing safety of trial subjects and potential subjects, and the continuing validity and scientific merit of The Bio-K Study.

### **E.12. Record Retention**

In compliance with the ICH/GCP guidelines, the sponsor, site lead investigator and site institution will maintain all Essential Documents (CRFs and source documents related to each study subject) as well as all study documents as specified in ICH/GCP Section 8 – Essential Documents for the Conduct of a Clinical Trial of Guideline for Good Clinical Practice E6: ICH Harmonised Tripartite Guideline. The site lead investigator and institution will take appropriate measures to prevent misplacement, accidental or premature destruction of study documents. The essential documents are grouped in three sections according to the stage of the trial during which they will normally be generated: 1) before the clinical phase of the trial commences, 2) during the clinical conduct of the trial, and 3) after completion or termination of the trial. Together, these essential documents constitute a trial master file to be established with the sponsor and at each site before it begins the clinical phase of the trial.

Essential documents must be retained until at least 2 years have elapsed since the formal discontinuation of clinical development of the investigational product related to this study. These documents will be retained for a longer period if required by local IRB/IEC or by an agreement with the sponsor. It is the responsibility of the sponsor to inform the investigator/institution as to when these documents no longer need to be retained.

In the event that the responsible site lead investigator retires, relocates, or for other reasons withdraws from the responsibility of keeping the study records, custody must be transferred to a person who will accept the responsibility. The sponsor must be notified in writing of the name and address of the new custodian at that site. Under no circumstance shall the investigator relocate or dispose of any study documents before having obtained written approval from the sponsor.

If it becomes necessary for the sponsor or the appropriate regulatory authority to review any documentation relating to this study, the site lead investigator/institution must permit access to such reports.

### **E.13. Study Completion and Termination**

The study is considered completed with enrollment of the 100th subject. The final data from the study site will be sent to the sponsor after completion of the final subject assessment at that study site.

The sponsor reserves the right to close the study site or terminate the study at any time for any reason at the sole discretion of the sponsor. Study sites will be closed upon study completion. A study site is deemed in closed status when all required study documents have been collected and a study-site closure visit has been performed by the designated investigator monitor.

The sponsor or site investigator monitor may initiate study-site closure at any time, provided there is reasonable cause and sufficient notice is given in advance of the intended termination. Reasons for the early closure of a study site by the sponsor or investigator may include but are not limited to failure of the investigator to comply with the protocol, the requirements of the IRB or local health authorities, the sponsor's procedures, or GCP guidelines, and inadequate recruitment of subjects by the investigator

### **E.14. Reportable Event – Reporting to Sponsor and Site IRB/IEC**

#### **Adverse Effects.**

Patients will be asked open ended questions about any adverse perceptual effects of ketamine during the infusion, such as visual hallucinations, dizziness, or vertigo, every 15 minutes during infusions and at 30- and 60 minutes after each infusion. Infusions will be stopped if side effects seem severe or if the patient wishes it to be stopped or infusion may also be stopped for any marked vital abnormality, as noted above. Side effects will also be monitored utilizing the Ketamine Side Effects Scale (KSES) [58] and the YMRS. The KSES and YMRS will be completed for the 40 min infusion, recorded at baseline, at 30 min during infusion, at 20 min post infusion stop (t60), at 60 min post infusion stop (t100). For the 100 min infusion, KSES and YMRS will be recorded at baseline; at 30, 60 and 100 minutes after start of infusion; and 60 minutes post infusion stop. The Repeatable Battery for the Assessment of Neuropsychological Status (RBANS) is administered in the acute phase at baseline (prior to the first ketamine infusion) and at 24 hours following the 3rd acute phase infusion, and in the optional continuous phase, at 24 hours after the 4th continuous phase infusion, to assess cognitive effects. See §E.8 for description of assessment measures.

The sponsor has established the Standard Operating Procedure in conformity with regulatory requirements to ensure appropriate reporting of Unanticipated Problem Involving Risk to Subjects or Others (UPIRTSO) and non-UPIRTSO events to the sponsor and local IRB/IEC. Including notification to local IRB/IEC of an UPIRTSO or non-UPIRTSO, each site is provided as a separate document the names and telephone numbers of individuals who should be contacted regarding safety issues and/or with questions regarding the study. In addition, each site will be provided an UPIRTSO form to be submitted to the sponsor describing the event, subject identification code, subject date of birth, and date seen.

An UPIRTSO is defined as any problem or event which, in the opinion of the local Investigator, meets all three of the following criteria:

1. Serious: Serious problems or events that result in significant harm, (which may be physical, psychological, financial, social, economic, or legal) or places subjects or others at a greater risk of harm than was previously known or recognized..

2. Unanticipated: A problem or event is "unanticipated" when it was unforeseeable at the time of its occurrence and is:
  - a. Not already described as a potential risk in the approved informed consent
  - b. Not already described as a potential risk in the approved protocol
  - c. Not listed in the Investigator's Brochure
  - d. Not part of an underlying disease
  - e. Occurred at an increased frequency or at an increased severity than expected,
3. Related: A problem or event is "related" if it is possibly related to the research procedures.

An UPIRTSO can include but isn't limited to adverse drug reactions (both serious and unexpected), adverse events, serious adverse events, protocol deviations and protocol violations occurring in this study meeting the criteria that the event was serious, unanticipated and related to study procedures. Reporting to sponsor and local IRB/IEC should occur as soon as possible and in accordance with local IRB/IEC reporting guidelines. In contrast, a non-UPIRTSO, although still reportable, is defined as a reportable event that does not meet all three criteria in the definition of an UPIRTSO.

An Adverse Drug Reaction is defined as an unexpected, unintended, undesired, or excessive response by a patient to a medication that could not have been prevented and having one or more of the following characteristics:

- Requires hospitalization
- Prolongs length of stay
- Requires use of antidote(s), prescription drug therapy, extra diagnostic activities, or other corrective therapeutic measures (e.g. monitoring, discontinue medication)
- Fatality or permanent disability
- Significantly complicates diagnosis
- Negatively affect prognosis
- Medication incompatibility not previously identified
- A serious reaction not listed on the product package insert

An Adverse Event is defined as any untoward medical occurrence in a patient or clinical investigation subject administered a pharmaceutical product and which does not necessarily have to have a causal relationship with this treatment.

A Serious Adverse Event is any untoward medical occurrence that at any dose results in death, is life-threatening, requires inpatient hospitalization or prolongation of existing hospitalization, results in persistent or significant disability/incapacity, a congenital anomaly/birth defect.

A Protocol Violation is defined as any change, divergence or departure from the study design or research procedures that is under the investigator's control and has not been approved by the local IRB/IEC. A Major Protocol Violation/Deviation is defined as any change that affects the rights and welfare of subjects and others, increases risks to subjects and others, decreases potential benefits, compromises the integrity or validity of the research, or represents willful or knowing misconduct to include not limited to enrolling subjects who did not meet the inclusion/exclusion criteria, performing study procedures not approved by the IRB, failure to obtain and/or document informed consent, and receipt of incorrect treatment or dose by a study subject. A Minor Protocol Violation/Deviation is any change that did not increase the risk or decrease the benefit or significantly affect the subject's rights, safety or welfare and/or the integrity of research data (e.g. a routine lab missed at a visit and re-drawn, shortening the duration between a planned study visit, using an outdated HIPAA form or consent form when there are no differences between the two forms other than the approval date).

A Protocol Deviation is defined as a limited prospective exception to the protocol (e.g. agreement between sponsor and investigator to enroll a single subject who does not meet all inclusion/exclusion criteria). Like protocol amendments, deviations initiated by the clinical investigator must be reviewed and approved by the local IRB/IEC and the sponsor prior to implementation, unless the change is necessary to eliminate apparent immediate hazards to the human subjects (21 CFR 312.66), or to protect the life or physical well-being of the subject (21 CFR 812.35(a) (2)).

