Depressive symptoms, response, remission, suicidality, and global clinical state will be assessed at baseline prior to each ketamine infusion, at the end of infusion (40 or 100 minutes), at the end of post-ketamine infusion observation (60 minutes), and 24 hours after each infusion during the acute and continuation phases, using standardized rating scales. Safety measures will include standardized questionnaires and an open-ended side effect questionnaire. Concerns that arise about worsening suicidality or other psychiatric emergencies will prompt further evaluation by a board certified study psychiatrist, who will determine the need for additional assessment and follow-up.

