**Table 1. Schedule of assessments (acute phase treatment)**

		Infusion number 1			Infusion number 2			Infusion number 3		
	Screening	Baseline	40 or 100 min	24h post	Before	40 or 100 min	24h post	Before	40 or 100 min	24h post

SCID	X									
PHQ-9	X	X								
SSF-II	X									
MADRS	X	X	X	X	X	X	X	X	X	X
BSS		X	X	X	X	X	X	X	X	X
SHPS		X		X						X
CGI-S		X			X			X		
CGI-C			X	X		X	X		X	X
SBP		Recorded at baseline, at Q15 minute intervals during infusions, at 30 minutes after end of each infusion, and at 60 minutes after end of each infusion								
DBP										
HR & RR										
SaO2										
TEAE										
		Infusion number 1			Infusion number 2			Infusion number 3		
		Baseline	40 or 100 min	24h post	Baseline	40 or 100 min	24h post	Baseline	40 or 100 min	24h post
KSES		For 40 min infusion, recorded at baseline, at 30 min during infusion, at 20 min post infusion stop, at 60 min post infusion stop. For 100 min, recorded at baseline; at 30, 60 and 100 minutes after start of infusion; and 60 minutes post infusion stop.								
YMRS										
RBANS		X								X
Key: BSS = Beck Scale for Suicidal Ideation; CGI-C = Clinical Global Impression, change subscale; CGI-S = Clinical Global Impression, illness severity subscale; DBP = diastolic blood pressure; HR = heart rate; RR = respiratory rate; KSES = ketamine side-effects scale; MADRS = Montgomery-Åsberg Depression Rating Scale; PHQ-9 = 9-item Patient Health Questionnaire; RBANS = Repeatable Battery for the Assessment of Neuropsychological Status; SaO2 = oxygen saturation; SBP = systolic blood pressure; SHPS = Snaith-Hamilton Pleasure Scale; TEAE = open-ended questionnaire to assess for treatment-emergent side-effects; YMRS = Young Mania Rating Scale.										

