**Clinical Assessments.**

Mood (MADRS) and suicide measures (BSS) will be obtained by the study coordinator at baseline, at the end of infusion (40-min or 100-min); and at 24 hours post-infusion time. Thus, there will be three clinical outcome assessment times for these measures per infusion. The Snaith-Hamilton Pleasure Scale (SHAPS) will be administered by the study coordinator at baseline, 24 hours following the first infusion, and 24 hours following the third (final) acute phase infusion. An investigator will complete a CGI-Severity of Illness (CGI-S) assessment at baseline before each infusion, and an investigator will complete a CGI-Global Improvement (CGI-C) assessment at the end of each infusion, and at 24 hours post-infusion for each infusion. See §E.8 for description of assessment measures.

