- **Ketamine Side Effects Scale:** This scale was developed to measure side effects to ketamine when administered for antidepressive effects [72].
- **Repeatable Battery for the Assessment of Neuropsychological Status:** The RBANS is a brief, standardized, individually administered battery to measure cognitive change in immediate memory, visuospatial/constructional orientation, language (naming, fluency), attention, and delayed memory. The 12 subtests that comprise the RBANS requires approximately 30 minutes to administer.

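### Dated side-effect questions stop 60 minutes after infusion stop (TEAE as read from the tables) and are not repeated at the 24-hour contact after the last infusion

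*Combined protocol and SAP*

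**What the plan says.** Section E.14 (Adverse Effects) dates the side-effect instruments in prose. The open-ended perceptual questions are asked "every 15 minutes during infusions and at 30- and 60 minutes after each infusion". For the 40-minute infusion, the last two KSES and YMRS points are "at 20 min post infusion stop (t60), at 60 min post infusion stop (t100", with t counted in minutes from infusion start. For the 100-minute infusion the schedule reads: "KSES and YMRS will be recorded at baseline; at 30, 60 and 100 minutes after start of infusion; and 60 minutes post infusion stop".

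A more general instrument is the one the Table 1 key describes as "TEAE = open-ended questionnaire to assess for treatment-emergent side-effects". Its row in Tables 1 and 4 carries no text of its own. It appears to share a merged cell with the vital signs, and that cell ends "at 30 minutes after end of each infusion, and at 60 minutes after end of each infusion". E.1 adds that "Safety measures will include standardized questionnaires and an open-ended side effect questionnaire", but gives no times.

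A 24-hour contact follows every infusion. E.6.b (Clinical Assessments) places MADRS and BSS there and adds: "an investigator will complete a CGI-Global Improvement (CGI-C) assessment at the end of each infusion, and at 24 hours post-infusion for each infusion". SHAPS is added after acute infusions 1 and 3. E.14 adds RBANS 24 hours after acute infusion 3 and after continuation infusion 4.

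**The concern.** Study staff already speak to the patient at 24 hours, but none of the side-effect instruments is on that contact's list. After the patient's last infusion there is no later baseline at which they would recur. A non-serious effect that starts after the first hour, such as headache or nausea, then reaches the database mainly if the patient mentions it or if it shows up in a rating made for another purpose. B.3 gives ketamine an elimination half-life of 2–3 hours, so questioning stops before one half-life has passed.

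What is at stake is the completeness of the side-effect record. The DSMB (E.11) advises on continuing safety, and E.16 plans descriptive statistics for most data elements. Both would rest on direct questioning for the clinic stay and on less systematic sources afterwards. No tolerability endpoint is planned, and the remission, response and biomarker analyses do not use these data.

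**Working it through.** The plan gives no figure to reproduce beyond its own time stamps, so the check sets the schedules side by side and does the clock arithmetic.

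**1. Last dated point after an infusion (E.14 prose; Tables 1 and 4)**

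- 40-minute infusion: 40 + 20 = t60 and 40 + 60 = t100. The stamps agree with the text, and the last point is t100.
- 100-minute infusion: 100 + 60 = t160.

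| Instrument | Last dated point | Placed at 24 h? | Source |
|---|---|---|---|
| KSES | stop + 60 min | no | E.14 prose |
| Open-ended perceptual questions | stop + 60 min | no | E.14 prose |
| TEAE | stop + 60 min, as read | no, as read | merged rows, Tables 1 and 4 |
| MADRS, BSS, CGI-C | 24 h | yes, every infusion | E.6.b, Tables 1 and 4 |
| RBANS | 24 h | acute 3 and continuation 4 only | E.14 |
| YMRS | stop + 60 min | unclear | E.14; E.9 says each rating visit |

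The TEAE line is the weakest. Table 4 as extracted also lacks the 24-hour RBANS mark that E.14 schedules, so a blank in that table is not proof of absence.

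**2. Time from the last dated question to the 24-hour contact**

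The documents do not say whether the 24 hours run from infusion start or stop.

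- From stop: 24 − 1 = 23 h.
- From start, 40-minute infusion: 24 − 100/60 = 22.3 h.
- From start, 100-minute infusion: 24 − 160/60 = 21.3 h.

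**3. Next baseline, where there is one (E.6, E.8.b)**

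- Acute phase: 1 to 4 days between infusions means infusions 2 to 5 days apart (days 1, 3, 5 up to days 1, 6, 11).
- First continuation infusion: 4–7 days after acute infusion 3. Later ones: 6–8 days apart.
- Overall: 2–8 days.

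**4. How many post-infusion intervals have no later dated question**

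- Acute completer without continuation: 3 infusions, of which 2 are followed by another baseline, leaving 1.
- Acute plus four continuation infusions: 7 infusions, of which 6 are followed by another baseline, leaving 1.
- Patient who stops early: the last infusion received, so 1.

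The clear gap is therefore one interval per patient, the last. For earlier infusions the next baseline may recover late effects, but the look-back period of the forms is not shown.

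**The case against.** The strongest reply is that several routes stay open after 60 minutes.

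- At 24 hours an investigator completes CGI-C, and a rating of 5 or 6 is a dropout criterion (E.18). BSS and, after the final acute and final continuation infusions, RBANS are also done. YMRS may be too, if E.9's wording on rating visits includes 24 hours.
- E.17 has patients asked openly about safety concerns, gives outpatients numbers to call, and describes 24-hour, seven-day inpatient team coverage.
- E.6.d requires an investigator evaluation before a patient leaves an outpatient infusion visit, with physical symptoms resolved. It also mentions outcome measures 1–2 hours after infusion, but names no side-effect instrument.
- Both UPIRTSO and non-UPIRTSO events are reportable without a one-hour limit (E.14).
- E.6.c offers an optional follow-up visit.

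Most of this stands, and it rules out a stronger reading. A reader might infer that serious events go unseen after the first hour; the documents do not support that. What remains is narrower. The 24-hour ratings cover global change, mood, suicidality, cognition and possibly mania, not general side effects. The E.17 question sits in the suicide plan and has no date. The follow-up visit has no listed content. The discharge check falls on the infusion day.

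A second fair point is that the risks named in B.4 are psychomimetic and hemodynamic, and the dense questioning around each infusion is aimed at these. No passage gives a rate of late-onset effects. That limits the importance of the gap without closing it.

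**Conclusion.** The point holds as an optional improvement. KSES and the perceptual questions end 60 minutes after infusion stop by explicit prose. TEAE ends there only on a reading of merged table rows. None is placed at the existing 24-hour contact. After each patient's last infusion this leaves about 21 to 23 hours before that contact without a dated side-effect question, and the contact itself does not ask one. Non-serious late-onset effects may be under-counted. The number missed is unknown, and no primary or biomarker result is affected.

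Three stronger inferences should be resisted:

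- That all seven possible 24-hour contacts (3 acute, 4 continuation) are equal gaps. All but the last are followed by a later baseline with KSES and, as read, TEAE.
- That 23 of 24 hours measures harm. It is clock time, and it assumes the 24 hours run from infusion stop.
- That all 100 patients are certainly affected. The 10 single-infusion Mayo patients (B.7) may be co-enrolled in a separate protocol whose side-effect schedule is not shown.

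The conclusion assumes that the unseen case report forms and sponsor procedure do not already require the question at 24 hours.

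**What to change.** For patients still to be treated, add the open-ended TEAE question, worded to cover any untoward event since the last contact, to the 24-hour contact after the last infusion, including for patients who drop out. E.6.c already refers to a 24-hour follow-up after infusion 1 or 2 for those who stop early, so the contact exists. Because the last infusion is not always known in advance, it is simpler to add the question to every 24h post column of Tables 1 and 4. KSES at 24 hours is optional. Tabulate effects up to 60 minutes separately from those between 60 minutes and 24 hours, so that the early figures stay comparable with data already collected.

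**Cost.** E.2 requires a sponsor amendment, investigator signature and site IRB approval. No new visit is needed, and E.6.d already allows the 24-hour assessment by telephone for inpatients discharged early. Asking time, at an assumed 2–5 minutes per contact, has these ceilings for a full trial:

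- Once per patient: 100 × 2/60 = 3.3 h to 100 × 5/60 = 8.3 h.
- Every acute contact, if all are completed: 90 × 3 + 10 × 1 = 280 contacts (one each for the 10 single-infusion patients) up to 100 × 3 = 300. That is 280 × 2/60 = 9.3 h to 300 × 5/60 = 25.0 h, plus up to 4 contacts per continuing patient.

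The real total would be lower, because an amendment cannot reach patients already treated and C.2.a records that recruitment has stopped at two sites. Extra elicited events also have to be recorded and reported (E.10, E.14), and the recorded side-effect rate would rise slightly. If an amendment is impractical, the trial report should say that scheduled side-effect questioning ended 60 minutes after infusion stop, once the TEAE timing has been confirmed.
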